## **7. BIOLOGICAL SAMPLING PROCEDURES**

All bloods done locally will be collected according to local sampling procedures. Procedures for collection, shipment and storage of blood samples for future biochemical and genetic analyses (collected at baseline and at 16 weeks after randomization) will be detailed in the study lab manual.

## **8. ETHICAL AND REGULATORY REQUIREMENTS**

The study will be conducted according to Good Clinical Practice Guidelines. Health Canada will be approached for the need to get Health Canada approval for this study. Investigators at each site will obtain approval of the protocol, informed consent form, advertisement and patient materials from local Research Ethics Boards prior to participant recruitment. Any changes to the protocol and informed consent form will need to be approved by local Research Ethics Boards ( $\pm$  Health Canada).

## **10. DATA MANAGEMENT**

Data management procedures will be outlined in the data management plan.

## **11. STATISTICAL METHODS AND SAMPLE SIZE DETERMINATION**

### **11.1 Proposed sample size and justification**

The sample size calculation is based on the estimated proportion of patients achieving diabetes remission of 10% in the control group. The control group estimate of 10% is based on the proportion of patients in the conventional diabetes treatment group of 13% who achieved FPG < 7.0 mmol/L and HbA1C < 6.2% off therapy after 2 years of follow-up observed in the Dixon *et al.* trial, after adjusting for the longer duration of diabetes since diagnosis in participants in our trial ( $\leq 8$  years versus < 2 years). A total sample size of 152 participants (76 per treatment group) will provide 80% power to show a risk difference of  $\geq 20\%$  in the induction of diabetes remission between treatment groups and 90% power to show a risk difference of  $\geq 23\%$ .

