## 1. INTRODUCTION

### 1.1 Background and rationale

The current approach to treating type 2 diabetes mellitus (T2DM) is to add progressively higher doses and numbers of glucose-lowering drugs to lifestyle approaches. People with type 2 diabetes are therefore taking such drugs from shortly after diagnosis until the end of their lives. A different, novel approach that intensively treats patients with several agents and lifestyle approaches for up to 2-4 months, followed by cessation of all drugs, may achieve a drug-free metabolic remission that could last for months to years. Such an approach has not been formally tested. However, a) evidence from small studies suggesting that approximately 40% of newly diagnosed patients can achieve a remission with short-term intensive treatment with insulin; b) a growing list of glucose-lowering drugs with novel mechanisms of action; and c) the appeal of remission-induction versus lifelong chronic therapy highlights the need to characterize strategies for metabolic remission of diabetes and to identify the optimal therapies and regimens for achieving remission.

We have just completed a peer-reviewed pilot trial of this approach at our centre. Eighty three people with T2DM diagnosed within the prior 3 years were randomized to 3 treatment groups: a) an 8-week intensive metabolic intervention; b) a 16-week intensive metabolic intervention; and c) standard diabetes therapy. The intensive metabolic intervention combined lifestyle therapy and basal insulin glargine, metformin and acarbose and aimed at achieving normoglycemia on therapy. We found that an 8-16-week course of therapy was safe and feasible and induced remission in up to 40% of people with early T2DM. These data illustrate that metabolic interventions such as the one proposed herein can be successfully implemented and have the potential to induce diabetes remission not requiring glucose-lowering therapies. The proposed multicentre randomized controlled trial will assess the remission-related efficacy of a sodium glucose co-transporter 2 (SGLT2) inhibitor-based regimen in a broader set of patients.

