### **6.2 Study outcomes**

#### **6.2.1 Primary and secondary outcomes**

The primary outcome is drug-free diabetes remission, defined as a HbA1C < 6.5% without use of glucose-lowering agents for at least 12 weeks. Related outcomes to be analyzed include complete diabetes remission, defined as a HbA1C < 6.0% without use of glucose-lowering agents for at least 12 weeks, and diabetes regression, defined as a HbA1C of 6.5-6.9% without use of glucose-lowering agents for at least 12 weeks.

HbA1C will be measured in the local labs at 12, 24, 36, 48 and 64 weeks after randomization, during which use of glucose-lowering medications will also be ascertained. FPG will also be measured in the local lab at 16 weeks. All FPG levels will be measured approximately 48 hours after the last dose of any glucose-lowering medication unless fasting capillary glucose rises above 12 mmol/L.

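### Does N = 152 fail because the 10% control remission rate comes from a stricter, later endpoint than this trial's own?

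*Combined protocol and SAP*

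**What the plan says.** Section 11.1 gives the source of its planning rate, an external trial: "The control group estimate of 10% is based on the proportion of patients in the conventional diabetes treatment group of 13% who achieved FPG" below 7.0 mmol/L and HbA1C below 6.2% off therapy at 2 years. It lowers that 13% to 10% "after adjusting for the longer duration of diabetes since diagnosis in participants in our trial" (up to 8 years, against under 2 years in the source). It then states: "A total sample size of 152 participants (76 per treatment group) will provide 80% power to show a risk difference of" at least 20 points, and 90% power for at least 23 points.

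Section 6.2.1 defines the endpoint actually tested: "The primary outcome is drug-free diabetes remission, defined as a HbA1C < 6.5% without use of glucose-lowering agents for at least 12 weeks". It has no fasting glucose condition. Section 11.2 reads it at 24 weeks, compares the arms with a chi-squared test at the 0.05 level, mentions no continuity correction, and counts anyone who drops out as not in remission. Section 5.4.3 expects losses to be minimal.

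Section 1.1 adds: "We have just completed a peer-reviewed pilot trial of this approach at our centre". It had three arms, the last two being "b) a 16-week intensive metabolic intervention; and c) standard diabetes therapy". Section 11.1 does not use that arm.

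**The concern.** The planning rate and the tested endpoint differ in three ways: the HbA1C limit (6.2% against 6.5%), the fasting glucose condition (present against absent) and the time of reading (2 years against 24 weeks). In one cohort at one time, the first two can only raise the remission rate here. The source limit is in fact nearer this trial's secondary outcome, "complete diabetes remission, defined as a HbA1C < 6.0% without use of glucose-lowering agents for at least 12 weeks", than its primary one. The single adjustment that is stated lowers the rate.

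Other features of the design also favour control remissions:

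- Inclusion criterion 4 (Section 4.1) sets no lower HbA1C limit for people already on drugs.
- Under Section 5.3.3, drugs stop at week 12 in both arms when HbA1C is below 7.3%.
- The primary reading follows 12 weeks later, and Section 5.3.3 itself notes that HbA1C lags behind glucose.

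For a fixed risk difference, a control rate nearer 50% means more variance and less power. If the true control rate were well above 10%, a real 20-point effect would be missed more often than the stated 20%. The pilot's standard-therapy arm looks like a closer source that was left unused.

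**Working it through.** **Inputs from the documents.** 76 per arm; control rate 10%; differences of 20 and 23 points (Section 11.1); chi-squared test, alpha 0.05 (Section 11.2), taken as two-sided.

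**Formula.** With control rate p1, intervention rate p2, d = p2 - p1 and m = (p1 + p2)/2:

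power = Phi{ [d x sqrt(n) - 1.96 x sqrt(2m(1 - m))] / sqrt(p1(1 - p1) + p2(1 - p2)) }.

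A continuity correction replaces d by d - 1/n.

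**The plan's own figures.**

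- 10% against 30%: (1.744 - 1.109)/0.548 = 1.16, power 87.7%; corrected, 82.9%.
- 10% against 33%: (2.005 - 1.139)/0.558 = 1.55, power 94.0%; corrected, 91.1%.

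The uncorrected formula needs a total of only 124 (80%, 20 points) or 130 (90%, 23 points). The corrected one needs 144 or 148. So 152 meets both stated powers at 10% control under either convention, and lies closest to a corrected calculation.

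**Highest control rate at which 76 per arm keeps the stated power.**

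| Convention | 80% for 20 points | 90% for 23 points |
|---|---|---|
| Plain, no loss | 16.9% | 15.4% |
| Corrected, no loss | 12.1% | 11.2% |

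**How far the HbA1C limit alone could move the rate.** Assume off-drug HbA1C is roughly normal, with an SD of 0.8 to 1.5 (not in the documents). If all controls are off drugs, the new rate is Phi(-1.2816 + 0.3/SD): 14.0% (SD 1.5), 16.3% (SD 1.0), 18.2% (SD 0.8). If only a share f is off drugs, it is f x Phi(z(0.10/f) + 0.3/SD). With f = 0.15 (also assumed) this gives 11.0%, 11.5% and 11.9% for the same SDs.

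**Power at those rates, 76 per arm, no loss.**

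| Control rate | 20 points, plain | 20 points, corrected | 23 points, plain |
|---|---|---|---|
| 11.0% | 86.4% | 81.4% | 93.2% |
| 14.0% | 83.0% | 77.6% | 91.0% |
| 16.3% | 80.6% | 75.0% | 89.4% |
| 18.2% | 78.8% | 73.0% | 88.1% |

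On the test the plan names and the losses it expects, the worst case in this range is 1.2 points under 80% and 1.9 points under 90%.

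**Loss to follow-up.** Suppose 10% are lost (assumed) and counted as failures. If both rates are multiplied by 0.9, power for 20 points at the four control rates is 81.5, 77.5, 74.7 and 72.6%. That also shrinks the tested difference to 18 points. Section 11.2 already makes dropouts non-remitters, so the planned difference can be read as including them. With 20 points kept on the analysed endpoint and control rates multiplied by 0.9, power is 87.8, 84.6, 82.2 and 80.5%.

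**What the pilot arm could add.** Splitting 83 equally over three arms (assumed) gives about 28. An illustrative 3/28 is 10.7%, with an exact 95% interval of 2.3% to 28.2%. That interval covers every limit in the first table.

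**The case for a change.** The strongest reply is that the range of 11-18% shifts only the HbA1C limit. The dropped glucose condition, the earlier reading, the missing HbA1C floor and the week-12 drug stop could take the control rate further. At 20% control, power for 20 points is 77.3% plain and 71.5% corrected; at 25% it is 73.9% and 67.9%. If 152 did come from a corrected calculation, the margin is only about two points of control rate, and the source's unadjusted 13% already gives 78.8%. On this view, enrolling 168 would be prudent, and Section 5.4.1's figures deliver that number within the planned window (7 sites x 2 per month x 12 months).

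Part of this stands. The input is unsupported for this endpoint, and the documents cannot bound the true rate. But the forces are not all one way. Under Section 5.3.3, participants at 7.3% or above at week 12, and those who relapse, receive standard glycemic management, so the all-off-drugs case behind 14-18% overstates the shift. Dropouts counted as failures also lower the rate.

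The remedies do not answer the question either. By the same formula, 168 still gives 79.7% and 77.9% (corrected), or 78.9% and 76.9% (10% loss, both rates scaled), at 16.3% and 18.2% control. Its only basis is recruitment capacity, from an approximate site count and an average rate. As for the pilot, Section 1.1 prints neither its control result nor its endpoint definition. Its patients were diagnosed within 3 years rather than 8, at one centre, so a judged duration adjustment would return. Section 12 also still describes the pilot as ongoing.

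Finally, if the intervention reached the pilot's upper figure of 40% (an assumption here), plain power with no loss at 16.3% and 18.2% control would be 90.9% and 84.7%.

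**Conclusion.** The mismatch is genuine, and 10% is more likely too low than too high. It is a gap in justification, not an error in the calculation. On the plan's own terms (a chi-squared test with no correction mentioned, two-sided as assumed here, and minimal loss), N = 152 absorbs a rise in the control rate from 10% to 16.9% before power for 20 points drops below 80%, and to 15.4% before power for 23 points drops below 90%. Over the assumed 11-18%, the largest shortfall is 1 to 2 points of power. A larger one requires a continuity correction, a 10% loss that also shrinks the effect, or a control rate near 20% or more. The documents establish none of these.

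No change follows. Naming the test convention and loss allowance would complete the record but leave the trial as it is. A larger N would be chosen without a shown shortfall. Re-scoring about 28 pilot participants could not tell 152 from 168. The conclusion rests on the assumed HbA1C spread (SD 0.8 to 1.5), normality and low loss; a reliable control rate above about 17% on this trial's definition would reopen it.

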### **11.2 Statistical analyses**

All group comparisons will be conducted according to the intention-to-treat principle with inclusion of data from all participants according to their treatment group assignment, regardless of adherence to therapy. The primary outcome in this study is the proportion of patients in the intervention group who achieve drug-free diabetes remission 24 weeks after randomization compared to the control group. The treatment groups will be compared using a chi-squared test with  $\alpha = 0.05$  level of significance. The outcome will be reported as a risk difference in the induction of remission between the intervention group and the control group with 95% confidence interval. Any individual who withdraws/drops out prior to the 24, 36, 48 and 64 week visit will be classified as not having achieved drug-free diabetes remission at that point in time. Participants who fail to achieve remission or have hyperglycemia relapse will be censored with respect to diabetes remission outcomes.

For secondary analyses, a chi-squared test will be used for dichotomous outcomes and a two-sample t-test (or a non-parametric equivalent) for continuous outcomes. Secondary outcomes will be used only for generation of new hypotheses. Clinical and metabolic predictors of the successful induction of diabetes remission will be evaluated using logistic regression modeling. We do not plan to perform any interim analyses in this trial.

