**Secondary research questions:**

- 1) Compared to the control group, does this therapeutic approach achieve drug-free diabetes remission in a higher proportion of patients than standard diabetes therapy at 36, 48 and 64 weeks after randomization?
- 2) Compared to the control group, does this therapeutic approach achieve drug-free HbA1C <6.0% in a higher proportion of patients than standard diabetes therapy at 24, 36, 48 and 64 weeks after randomization?
- 3) Compared to the control group, does this therapeutic approach achieve drug-free diabetes regression in a higher proportion of patients than standard diabetes therapy at 24, 36, 48 and 64 weeks after randomization? Diabetes regression is defined as HbA1C 6.5-6.9% off glucose-lowering agents for at least 12 weeks.
- 4) What HbA1C levels are achieved in the intervention group and the control group at 12, 24, 36, 48 and 64 weeks after randomization?
- 5) What rates of hypoglycemia are observed in the intervention group and the control group during 64 weeks of follow-up?
- 6) What is the change in weight, body mass index (BMI), waist circumference and waist/hip ratio from baseline to 12, 24, 36, 48 and 64 weeks in the intervention group and the control group?
- 7) Are age, gender, ethnicity, diabetes duration, smoking, family history of diabetes, baseline BMI, waist circumference, HbA1C or fasting plasma glucose (FPG) determinants of diabetes remission at 24 weeks after randomization?

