## **5. STUDY CONDUCT**

### **5.1 Screening and baseline evaluation**

At the screening assessment, informed consent will be obtained, and eligibility criteria will be assessed by performing an interview and physical examination. Blood will be drawn for creatinine, ALT, fasting plasma glucose (FPG), and HbA1C. Fasting serum samples will also be taken for storage at the screening visit in participants who agree to it. A urine pregnancy test (urine BhCG) will be performed in women with childbearing potential. A baseline electrocardiogram (ECG) will also be performed to assess for any evidence of ischemic heart disease or arrhythmia. Baseline weight, height, body mass index, waist circumference and hip circumference will be obtained in all study participants. Physical activity and food frequency questionnaires will also be administered at baseline.

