#### **5.3.3 Monitoring for hyperglycemia relapse during the maintenance phase of the trial**

In all participants, HbA1C will be drawn during week 12 of the trial. At the end of week 12, glucose-lowering medications will be discontinued in all participants with a HbA1C <7.3%, and insulin will be tapered over a 5-day period. Participants will be encouraged to continue with lifestyle modifications and regular home glucose monitoring (i.e. at least 5 fasting capillary measures per week). They will meet with research staff every 2-4 months during the maintenance phase of the trial to review any challenges in achieving and maintaining exercise and weight loss goals. Participants will be assessed by research staff every 1-2 months by telephone to review adherence to lifestyle therapy, SMBG readings and to screen for symptoms of hyperglycemia.

It is possible that glucose levels may quickly rise after glucose-lowering drugs are stopped in some of the participants whose HbA1C is <7.3% on these drugs. This rise may not be detected with HbA1C levels due to the well-known time-lag between rising glucose levels and rising HbA1C levels.

In light of the above, hyperglycemia relapse will be defined as follows:

- a. a HbA1C  $\geq$  7.0% at 24, 36, 48 and 64 weeks; or
- b. reinitiation of glucose-lowering drugs; or

- c. capillary glucose values  $\geq 10$  mmol/L on  $\geq 50\%$  of SMBG readings over 1 week in the absence of an acute illness.

All participants identified to have hyperglycemia relapse will receive standard glycemic management according to the judgment of their physician or investigator. Participants found to have HbA1C  $\geq 7.3\%$  on therapy during week 12 of the trial will also receive standard glycemic management. These participants will continue to be contacted by telephone every 1-2 months to review SMBG readings, medication adherence and side effects.

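### Section 11.2's censoring sentence contradicts its own intention-to-treat rule for a yes/no outcome and needs replacing; separately, adjusting the primary comparison for baseline HbA1C is a cheap, modest gain

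*Combined protocol and SAP*

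**What the plan says.** Section 11.2 sets the primary comparison at 24 weeks: "The treatment groups will be compared using a chi-squared test", at the 0.05 level, with a risk difference and 95% confidence interval. Three rules in the same paragraph decide who is counted:

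- intention-to-treat, with "inclusion of data from all participants according to their treatment group assignment";
- anyone who drops out before a visit "will be classified as not having achieved drug-free diabetes remission at that point in time";
- a third rule, which covers people still in follow-up and uses the language of time-to-event analysis: "Participants who fail to achieve remission or have hyperglycemia relapse will be censored with respect to diabetes remission outcomes".

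Section 6.2.1 defines remission by HbA1C below 6.5% and at least 12 weeks off glucose-lowering drugs. Section 5.3.3 introduces a separate list with "hyperglycemia relapse will be defined as follows": (a) HbA1C of 7.0% or more at a scheduled visit, (b) restarting drugs, or (c) a week of high home glucose readings.

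On baseline data, section 5.1 says of screening: "Blood will be drawn for creatinine, ALT, fasting plasma glucose (FPG), and HbA1C". Table 1 in Appendix A shows HbA1C at week -1 for both groups. Secondary question 7 in section 1.2 lists among its candidate predictors "baseline BMI, waist circumference, HbA1C or fasting plasma glucose (FPG) determinants of diabetes remission at 24 weeks after randomization". Section 11.2 uses logistic regression only for that predictor question. Continuous secondary outcomes get "a two-sample t-test (or a non-parametric equivalent) for continuous outcomes".

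Section 11.1 gives 76 per group, a 10% control rate, 80% power for 20 points and 90% for 23 points. It states no sidedness, continuity correction or loss allowance.

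**The concern.** A chi-squared comparison of proportions needs a denominator, and section 11.2 gives two that disagree. The first two rules keep all 152 participants. The third, if it means removal, drops people because of their outcome, and then neither a chi-squared test nor an adjusted model compares the groups as randomised. An analyst could apply either reading and claim to have followed the plan.

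The second matter is efficiency, not validity. The outcome dichotomises HbA1C, and entry values range widely. Under section 4.1 an untreated participant may enter anywhere from 6.5% to 9.5%, so needs a fall of 0.1 to 3.1 points to read 6.4%. Those on drugs may enter at 8.0% or below, with no lower limit. If baseline HbA1C predicts remission, the unadjusted test gives up precision in a small trial.

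**Working it through.** **1. The plan's own power figures.** Inputs from section 11.1: n = 76 per group, 10% versus 30% and 10% versus 33%. Two-sided 0.05 is assumed. With d the risk difference and p̄ the mean of the two rates:

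power = Φ{[d − 1.96√(2p̄(1−p̄)/n)] / √([p₁(1−p₁)+p₂(1−p₂)]/n)}

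For 20 points: (0.200 − 1.96 × 0.0649)/0.0628 = 1.16, which gives 87.7%. For 23 points: (0.230 − 1.96 × 0.0666)/0.0640 = 1.55, which gives 94.0%.

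| Assumption | 20 points | 23 points |
|---|---|---|
| Stated in 11.1 | 80% | 90% |
| Uncorrected, no loss | 87.7% | 94.0% |
| Continuity correction (d − 1/n), 5% loss (n = 72.2) | 80.6% | 89.5% |
| Uncorrected, 15% loss excluded (n = 64.6) | 81.9% | 89.8% |

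The stated figures can therefore be matched in at least two ways, and the documents do not say which was used.

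**2. The denominator.** Take each possible week-24 status in turn:

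| Status at week 24 | In remission (6.2.1)? | Relapse (5.3.3)? | Reached by the censoring sentence? |
|---|---|---|---|
| HbA1C <6.5%, off drugs 12 weeks | Yes | No | No |
| HbA1C 6.5-6.9%, off drugs | No | No | Yes, not in remission |
| HbA1C ≥7.0% | No | Yes (a) | Yes |
| Drugs restarted | No | Yes (b) | Yes |
| Criterion (c) met, no drug restarted, HbA1C <6.5% | Yes | Yes (c) | Yes |

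Read literally as removal, only the first row survives, so each group shows 100%. No comparison is left.

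A narrower reading removes relapsers only. Its effect depends on relapse rates that the documents do not give. Two illustrations under assumed rates:

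- True 10% versus 30%, half of non-remitters removed in each group: 7.6/(7.6 + 34.2) = 18% versus 22.8/(22.8 + 26.6) = 46%. A 20-point difference becomes 28.
- True 20% in both groups, 30% of control and 60% of intervention non-remitters removed: 15.2/(15.2 + 42.56) = 26% versus 15.2/(15.2 + 24.32) = 38%. This is a false 12-point difference.

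By simulation at 10% true remission in both groups, the same 30% versus 60% removal raises the null rejection rate from 5.1% to 17.9%.

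**3. Adjusting for baseline HbA1C.** The prognostic strength is not in the documents, so it is varied. The simulation used 12,000 runs per setting, 152 participants, simple 1:1 allocation and true remission of 10% versus 30%. HbA1C was standard normal. Drug-use and site effects were also present in the generated data. The adjusted analysis is a logistic model on treatment and HbA1C, giving a standardised risk difference with a leverage-corrected standard error.

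| Log-odds per SD (odds ratio) | Chi-squared power | Adjusted power | Change (points) |
|---|---|---|---|
| 0 (1.0) | 87.7% | 87.3% | −0.4 |
| 0.5 (1.6) | 88.5% | 89.0% | +0.5 |
| 1.0 (2.7) | 88.1% | 91.3% | +3.2 |
| 1.4 (4.1) | 88.7% | 93.7% | +5.0 |

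Two further simulations of the HbA1C-only model gave −0.7/+0.6/+2.7/+5.5 and −0.3/+0.8/+3.4/+5.1. Their null rejection rates for the adjusted analysis were 4.6-5.0% and 4.4-5.3%. Adding baseline drug use gave 86.9/88.9/91.1/93.5%, no better than HbA1C alone. In that larger model an ordinary robust standard error rejected 5.4-6.3% under the null, which is why the leverage correction is specified. Non-convergence occurred in 0.1% of runs at 10% versus 30%, and in at most 0.7% at 10% versus 10%.

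**4. Continuous secondary outcomes.** Assume equal variances and a baseline-to-follow-up correlation r. The ANCOVA variance is (1 − r²) times that of a t-test on follow-up values and (1 + r)/2 times that of a t-test on change. At r = 0.3, 0.5 and 0.7 the reductions are 9%, 25% and 49% against follow-up, and 35%, 25% and 15% against change.

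**The case against.** **The authors probably meant failure, not removal.** Full removal gives 100% versus 100%, which cannot be intended beside an all-participants rule and a reported risk difference. That is fair, and a reader should not infer that the sponsor will drop non-remitters: the documents do not say so. What stands is that the sentence does not say what is meant, and its only literal reading is unusable.

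**The partial-removal figures rest on invented relapse rates.** Correct. They show that the distortion can be large and can run in either direction. They do not predict this trial's result.

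**Adjustment is a preference.** Largely right. One might infer that an unadjusted chi-squared test is a flaw. It is not: with the full denominator it rejected 4.8-5.5% under the null. Chance imbalance in HbA1C is not bias, and the planned interval already allows for it. The gain may be nil, and the top of the range needs an odds ratio of about 4 per SD. The simulation's normal HbA1C also ignores the eligibility bounds. What stands is that the covariate is already collected and the cost is small.

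**Drug use and site.** A drug-use term showed no gain. Section 5.2.1 describes a schedule per site but is silent on blocking, so nothing is claimed about site terms.

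**Power.** A reader might take 87.7% against 80% as an arithmetic error or a reason to change the sample size. Neither follows, because ordinary assumptions reproduce the stated figures.

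**Secondary outcomes are only hypothesis-generating.** True, so ANCOVA is a minor improvement.

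**Conclusion.** The censoring sentence is wrong as written. It conflicts with the two rules before it, and applied literally it leaves nothing to test. This part needs no assumption. The size of the harm under a partial reading does depend on assumed relapse rates and cannot be fixed from the documents.

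Leaving out baseline HbA1C is a missed cheap improvement, not an error. Adjustment is worth about -1 point of power if HbA1C is not prognostic, and about +0.5, +3 and +5 points at 0.5, 1.0 and 1.4 log-odds per SD, with type I error kept at about 5%. These figures rest on the assumed strengths and on 10% versus 30% remission.

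The silence in section 11.1 is an optional point of reporting. The stated power is conservative for a plain two-sided test with no loss.

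**What to change.** 1. Replace the censoring sentence with: *All randomised participants remain in the denominator at every visit; anyone who does not meet the section 6.2.1 definition of drug-free remission at that visit, including because glucose-lowering drugs were restarted, is counted as not in remission at that visit.* This keeps the existing endpoint and judges status afresh at each visit. If the sponsor wants relapse by home glucose readings (criterion c) to count as failure, sections 5.3.3, 6.2.1 and 11.2 must be reconciled to say so.

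2. Prespecify as the primary analysis a logistic regression on treatment and continuous baseline HbA1C. Report the standardised risk difference with a 95% interval from a leverage-corrected robust standard error. Use the unadjusted risk difference if the model does not converge, and keep the chi-squared test as supportive. A baseline drug-use term is optional.

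3. Use ANCOVA on the baseline value for continuous secondary outcomes in place of the two-sample t-test.

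4. Optionally, state in section 11.1 the sidedness, the continuity correction if any, and the loss allowance. No change in sample size.

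Cost: item 1 is wording only. Items 2 and 3 need slightly more code and no new data. Item 2 can lose up to about 1 point of power if HbA1C is not prognostic. With only about 30 remissions expected (7.6 + 22.8), the corrected standard error and the fallback are needed.

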### **5.4.3 Losses to follow-up**

Losses to follow-up are expected to be minimal as the study duration is only 64 weeks. The investigators will make every effort to contact participants who are lost to follow-up. In order to minimize losses to follow-up, participants who do not adhere to the assigned treatment or visit schedule will be encouraged to do HbA1C measurements through their regular diabetes care provider and will be contacted by telephone to collect key data. Participants who withdraw consent will be asked to return any study drugs to the study centre and encouraged to return to their regular diabetes care provider for assessment and further care.

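### Section 11.2 plans unadjusted two-sample tests for HbA1C and the anthropometric outcomes; a baseline-adjusted repeated-measures model would use data already collected and gain some precision at almost no cost

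*Combined protocol and SAP*

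**What the plan says.** Section 11.2 gives one method for continuous secondary outcomes: "a two-sample t-test (or a non-parametric equivalent) for continuous outcomes". It names no covariate, no longitudinal model and no rule for missing continuous values. Its rule that drop-outs count as failures covers remission only. The same paragraph adds: "Secondary outcomes will be used only for generation of new hypotheses".

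The secondary research questions in 1.2 define the two groups of outcomes differently:

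- Question 4 concerns levels: "What HbA1C levels are achieved in the intervention group and the control group at 12, 24, 36, 48 and 64 weeks after randomization".
- Question 6 concerns changes: "What is the change in weight, body mass index (BMI), waist circumference and waist/hip ratio from baseline", at the same five weeks.

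Table 1 in Appendix A schedules HbA1C in both arms at screening and at weeks 12, 24, 36, 48 and 64. Weight, waist and hip are scheduled before treatment and, in both arms, at weeks 6, 12, 16, 24, 36, 48 and 64. BMI follows from weight and the screening height. Other continuous outcomes have a different pattern: FPG has a screening value and one follow-up at week 16, and the six-point glucose profiles (weeks 6 and 12) have no baseline.

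On losses, section 5.4.3 anticipates few. For participants who do not keep to treatment or visits, it says they will be encouraged to have HbA1C measured by their usual diabetes care provider and "will be contacted by telephone to collect key data".

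**The concern.** A two-sample test cannot combine visits. With five time points it therefore implies five separate comparisons per outcome, although 11.2 does not say so in words. Two consequences follow.

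The first is precision. Baseline HbA1C usually predicts later HbA1C, and a comparison of raw levels leaves that variation, and any chance imbalance at baseline, in the estimate. Entry HbA1C can vary a good deal, since 4.1 admits 6.5–9.5% off drugs, or up to 8.0% on up to two agents. A change score removes baseline by subtraction, which is less efficient than regression whenever r is below 1.

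The second is missing data. A comparison at one visit includes only people with a value at that visit, even where earlier values are on file. This sits uneasily with the intention-to-treat commitment in 11.2 to include everyone's data. If those who stop attending differ in glycemia between the arms, the estimate could shift.

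At stake are the HbA1C and anthropometric estimates and their confidence intervals. The primary chi-squared comparison is not involved.

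**Working it through.** **The plan's own figures.** The plan states no power or precision for any continuous outcome. The 80% and 90% in 11.1 belong to the binary primary outcome. They reproduce with a continuity-corrected formula and an assumed 5% loss (76 × 0.95 = 72.2 evaluable per arm: 80.6% for 10% v 30%, 89.5% for 10% v 33%). They do not bear on this point.

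**Inputs.** n = 76 per arm (11.1). The SD σ and the baseline-to-visit correlation r are not in the documents. I take σ as equal at baseline and follow-up, and r from 0.3 to 0.9.

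**Variance of the difference between arms, complete data**

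- t-test on levels: 2σ²/n
- t-test on changes: (2σ²/n) × 2(1 − r)
- ANCOVA on baseline: (2σ²/n) × (1 − r²)

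The ratio of ANCOVA to levels is 1 − r². The ratio of ANCOVA to changes is (1 − r²)/[2(1 − r)] = (1 + r)/2.

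| r | v levels: variance ratio | SE falls by | n per arm matching 76 | v changes: variance ratio | SE falls by | n per arm matching 76 |
|---|---|---|---|---|---|---|
| 0.3 | 0.91 | 5% | 69 | 0.65 | 19% | 49 |
| 0.5 | 0.75 | 13% | 57 | 0.75 | 13% | 57 |
| 0.7 | 0.51 | 29% | 39 | 0.85 | 8% | 65 |
| 0.9 | 0.19 | 56% | 14 | 0.95 | 3% | 72 |

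For HbA1C levels, the difference detectable with 80% power at 76 per arm is 0.454 SD without adjustment. With adjustment it is 0.434, 0.394, 0.325 and 0.198 SD at r = 0.3, 0.5, 0.7 and 0.9.

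**What the other visits add.** With complete data, a repeated-measures model with unstructured covariance and baseline-by-visit terms gives essentially the ANCOVA estimate at each visit. The other visits help where values are missing. A simulation of 400 trials (SD 0.9, correlation 0.65 between later visits, 11% missing at week 64 in both arms) gave model-to-t-test variance ratios of 0.86 at r = 0.3 and 0.72 at r = 0.5. These are close to the 0.91 and 0.75 from baseline adjustment alone, so most of the gain comes from baseline.

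**Bias under drop-out.** The drop-out rates here are assumptions, because the plan gives none. Drop-out was driven by the last HbA1C. The first three rows assume SD 0.8 and r = 0.6; the last assumes SD 0.9.

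| Drop-out mechanism | True difference | Loss | t-test mean |
|---|---|---|---|
| Same in both arms | 0 | about 5% to 28% | about 0 |
| Same in both arms | −0.30 | about 5%; 12–16%; 21–27% | −0.293; −0.28; −0.27 |
| Glycemia-driven in one arm only | 0 | 11% v 16%; 21% v 27% | −0.07; −0.13 |
| Glycemia-driven in intervention arm only | −0.30 | 19% v 11% | −0.355 |

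The last row overstates the effect by 0.055/0.30 = 18%. The repeated-measures model was within 0.006 of the truth in the first three rows and averaged −0.295 in the last. These data were generated as missing at random, which is the assumption the model needs, so its good performance here is partly by construction.

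**The case against.** An unadjusted t-test is a valid comparison in a randomized trial with complete data. The outcomes are declared hypothesis-generating and question 4 is nearly descriptive. The gain may also be small. Glucose-lowering drugs are changed and then stopped between baseline and follow-up, so r for HbA1C may be low, and at r = 0.3 the standard error falls by only 5%. Weight may have a high r, and at r = 0.9 the gain over change scores is 3%. All of this stands. It limits the point to efficiency and keeps its weight low.

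A reader might infer that the plan discards baseline for all these outcomes. It does not: question 6 asks for "change in weight, body mass index (BMI), waist circumference and waist/hip ratio from baseline", so baseline is ignored only for HbA1C. Nor do all continuous outcomes have a baseline and five follow-up visits, as FPG and the glucose profiles show.

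A reader might also infer that the planned comparisons are biased because drop-out could depend on glycemia. That dependence alone is not enough. With the same mechanism in both arms the bias was about zero under no effect, and a true effect was slightly attenuated. The 18% overstatement needs glycemia-driven loss in one arm only, at 11–19% missing. The documents give no ground for such rates. Section 5.4.3 expects few losses and offers a route to HbA1C through usual care, Table 1 schedules the same contacts in both arms from week 12.5 to week 64, and relapse leads to standard care rather than withdrawal. What remains is that 5.4.3 names no equivalent route for weight, waist or hip measurements, and 11.2 has no missing-data approach for continuous outcomes.

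**Conclusion.** The point holds as a minor improvement in precision. Section 11.2 leaves baseline HbA1C unused, uses the anthropometric baselines only by subtraction, and leaves the other visits unused throughout. Baseline adjustment would reduce the variance by 9% to 25% for HbA1C levels if r is 0.3 to 0.5, and by 15% down to 5% for change scores if r is 0.7 to 0.9. The formulas are standard; the correlations are assumptions. Bias from drop-out is a conditional risk: under 0.01 HbA1C points at about 5% loss with a common mechanism, and roughly 0.05 to 0.13 points only if loss reaches 11–27% and is glycemia-driven in one arm alone. Nothing here touches the primary test or the sample size.

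**What to change.** In 11.2, replace the t-test clause with wording such as:

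> HbA1C and the anthropometric outcomes will be analysed with a linear mixed model for repeated measures using all available visits, with arm-by-visit, baseline-by-visit and site terms and an unstructured covariance. Adjusted mean differences with 95% confidence intervals will be reported at weeks 12, 24, 36, 48 and 64. FPG at week 16 will be analysed by ANCOVA on the screening value. Outcomes without a baseline, such as the glucose profiles, will be compared by t-test.

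The site term matches the site-specific randomization schedules in 5.2.1. The text should also say which weight is the baseline, since Table 1 records one at screening and one at randomization.

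The cost is one paragraph, with no new data, visits or participants. The model is somewhat more complex and assumes that missing values are missing at random, which should be stated. It does not settle how HbA1C measured after glucose-lowering drugs are restarted is to be interpreted. Neither does the t-test, and that needs its own sentence.
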